# 13.3 Secondary Endpoint Definitions

- Safety and tolerability will be defined by frequency of the drug-related adverse events by grade as assessed by the NCI CTCAE Version 5.0, lab measurements, and vital signs.
- Radiographic progression will be defined as soft tissue disease progression by modified RECIST criteria 1.1 (baseline LN size must be >1.0 cm to be considered target or evaluable lesion) or by development of two or more new bone lesions not consistent with tumor flair for prostate cancer working group 3. Radiographic progression free survival (rPFS) is defined as the number of months from initiation of therapy to date of first radiographic progression, death from any cause, or last patient evaluation. Patients who have not progressed or died will be censored at the last date they were assessed and deemed progression-free.
- Time to PSA doubling from baseline is a time-to-event outcome. Time is measured from the initiation of therapy until the PSA has increased to 200% of baseline value, and confirmed with another measurement at least 4 weeks later, or death. The date of PSA doubling will be the first value recorded (not the confirmatory value).
- PSA PFS is defined as time to first PSA failure (two consecutive increases in PSA of 50% and ≥5 ng/mL above nadir) or death.
- OS is defined as the number of months from initiation of therapy to death due to any cause.

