# 7.4.1 Disease Progression

Progression will be evaluated on the basis of biochemical, radiographic, or symptomatic progression based on PCWG3 criteria, or by PSA doubling from baseline. Determinations of disease progression will be made by the investigator.

Progression will be defined as follows:

- 1. Radiographic progression defined by at least one of the following:
  - Soft tissue disease progression by modified RECIST criteria v.1.1 (See Appendix E)
  - Development of two or more new bone lesions not consistent with tumor flare per PCWG3. (If unclear, can repeat a bone scan in 6 weeks.)
- 2. Symptomatic or clinical progression defined by one of the following:
  - Development of a skeletal related event (SRE) defined as pathologic fracture, spinal cord or nerve root compression, palliative radiation to bone, or surgery to bone
  - Worsening pain due to CRPC unable to be controlled by non-narcotic or narcotic medications
  - Sustained worsening of ECOG status resulting from CRPC (e.g., 2 to 3)
  - Treating physician decided to initiate new systemic anti-cancer therapy
- 3. PSA doubling from baseline value, confirmed by a second value at least 4 weeks apart, with a minimum time since initiation of therapy of 12 weeks

We will encourage investigators to continue study treatment until radiographically confirmed disease progression or PSA doubling from baseline requires initiation of new systemic antineoplastic therapy.

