## 13.8 Analysis of Secondary Endpoints

The **safety analysis** will be performed in all subjects receiving combination olaparib and IV ascorbic acid. AE data will be listed individually and incidence of AEs summarized by system organ class and preferred terms within a system organ class for each treatment group. When calculating the incidence of AEs, each AE (based on preferred terminology defined by Medical Dictionary for Regulatory Activities (MedDRA; Version 13.1, or later) will be counted only once for a given subject. In analyses of grade and causality, if the same AE occurs on multiple occasions, the highest grade and strongest relationship to study drug will be assumed. If 2 or more AEs are reported as a unit, the individual terms will be reported as separate experiences. Changes in vital signs, hematology and clinical chemistry parameters from baseline to the end of the study will be examined. Toxicity will be tabulated by type and grade. Toxicities will be characterized according to the CTCAE version 5.0 Treatment-emergent changes from normal to abnormal values in key laboratory parameters will be identified.

Radiographic progression-free survival (**rPFS**) is defined as the number of months from initiation of therapy (cycle 1, day 1) to date of first radiographic progression, death from any cause, or last patient evaluation. Patients must receive at least one dose of olaparib and IV ascorbic acid to be considered evaluable. Radiographic progression will be determined by modified RECIST criteria 1.1 by development of two or more new bone lesions not consistent with tumor flair for prostate cancer working group 2. Patients who have not progressed or died will be censored at the last date they were assessed and deemed progression-free. rPFS will be summarized and six month estimates for rPFS will be reported using the Kaplan-Meier method with 90% confidence intervals.

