# APPENDIX E: Modified Response Evaluation Criteria in Solid Tumors (RECIST) 1.1 Criteria for Evaluating Response in Solid Tumors

RECIST version 1.1 will be used in this study for assessment of tumor response. While either CT or MRI may be used utilized, as per RECIST 1.1, CT is the preferred imaging technique in this study.

The RECIST 1.1 criteria have been modified specifically for this study so a lymph node will be considered pathological if it measures >20 mm in the short axis as opposed to the standard >15 mm cut off.

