#### **Disease Parameters**

Measurable disease: Measurable lesions are defined as those that can be accurately measured in at least one dimension (longest diameter to be recorded) as  $\geq 20$  mm by chest x-ray, as  $\geq 10$  mm with CT scan, or  $\geq 10$  mm with calipers by clinical exam. All tumor measurements must be recorded in millimeters (or decimal fractions of centimeters).

Note: Tumor lesions that are situated in a previously irradiated area might or might not be considered measurable unless there is evidence of progression in the irradiated site. Malignant lymph nodes. To be considered pathologically enlarged and measurable, a lymph node must be  $\geq 20$  mm in short axis when assessed by CT scan (CT scan slice thickness recommended to be no greater than 5 mm). At baseline and in follow-up, only the short axis will be measured and followed.

Non-measurable disease: All other lesions (or sites of disease), including small lesions (longest diameter <10 mm or pathological lymph nodes with ≥10 to <20 mm short axis), are considered non-measurable disease. Bone lesions, leptomeningeal disease, ascites, pleural/pericardial effusions, lymphangitis cutis/pulmonitis, inflammatory breast disease, and abdominal masses (not followed by CT or MRI), are considered as non-measurable.

Note: Cystic lesions that meet the criteria for radiographically defined simple cysts should not be considered as malignant lesions (neither measurable nor non-measurable) since they are, by definition, simple cysts.

'Cystic lesions' thought to represent cystic metastases can be considered as measurable lesions, if they meet the definition of measurability described above. However, if non-cystic lesions are present in the same subject, these are preferred for selection as target lesions.

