# **Evaluation of Target Lesions**

Complete Response (CR): Disappearance of all target lesions. Any pathological lymph nodes (whether target or non-target) must have reduction in short axis to <10 mm.

Partial Response (PR): At least a 30% decrease in the sum of the diameters of target lesions, taking as reference the baseline sum diameters.

Progressive Disease (PD): At least a 20% increase in the sum of the diameters of target lesions, taking as reference the smallest sum on study (this includes the baseline sum if that is the smallest on study). In addition to the relative increase of 20%, the sum must also demonstrate an absolute increase of at least 5 mm. (Note: the appearance of one or more new lesions is also considered progressions).

Stable Disease (SD): Neither sufficient shrinkage to qualify for PR nor sufficient increase to qualify for PD, taking as reference the smallest sum diameters while on study.

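### The rPFS definition is internally inconsistent: Section 13.3 and Appendix E give different lymph-node thresholds, and Section 13.8 drops the soft-tissue criterion and cites a different working group.

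*Combined protocol and SAP*

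**What the plan says.** **Nodes.** Section 13.3 bases rPFS on soft-tissue progression by modified RECIST 1.1, with the note that "baseline LN size must be >1.0 cm to be considered target or evaluable lesion". It does not say which axis is measured. Section 7.4.1 also uses modified RECIST 1.1 and refers to Appendix E. The opening of Appendix E states the study's modification: "a lymph node will be considered pathological if it measures >20 mm in the short axis". Its Disease Parameters section requires at least 20 mm in short axis on CT for a node to be measurable, and adds that "pathological lymph nodes with ≥10 to <20 mm short axis), are considered non-measurable disease". Only measurable lesions can be target lesions.

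**Bone.** Section 7.4.1 lists bone as a separate criterion: "Development of two or more new bone lesions not consistent with tumor flare per PCWG3". Section 13.3 has the same two-lesion rule, joined by *or* to the soft-tissue criterion, and cites working group 3. Section 7.4 also separates RECIST from bone progression and cites group 3. Section 13.8 reads: "Radiographic progression will be determined by modified RECIST criteria 1.1 by development of two or more new bone lesions not consistent with tumor flair", and then cites working group 2. The study calendar in Section 7.1 gives RECIST 1.1 or PCWG2.

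**New lesions.** In Appendix E, under target lesions, "the appearance of one or more new lesions is also considered progressions". The note does not say whether bone is excluded.

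**Use.** Section 13.8 summarises rPFS by Kaplan-Meier, with a six-month estimate and 90% confidence intervals. Section 7.4.1 leaves the determination of progression to the investigator, and Section 3.0 describes a multi-center study.

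**The concern.** Two places define the same modified RECIST and give node sizes that differ by a factor of two. Whether a node is a target matters because the two classes have different tests for progression. Target lesions progress on a measured change in their sum. Non-target lesions must show unequivocal progression that reflects overall disease status and not growth of one lesion.

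Investigators at several sites make the call, so two sites could score similar scans differently and each be following the document. The rPFS estimate would then depend partly on which section was used. rPFS is a secondary endpoint and one of the two outcomes named for the exploratory correlates. Radiographic progression is also among the criteria in Section 7.4 for ending treatment.

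**Working it through.** The documents give no sample size, event target or power for rPFS, so there is no figure of theirs to reproduce. The check applies Appendix E's own target-lesion test to example measurements. **The lesion sizes are assumed; the documents give none.**

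**Inputs**
- Target progression (Appendix E): increase in the sum of target diameters of at least 20% over the smallest sum, and at least 5 mm.
- Node threshold A (13.3, if read as a target threshold): over 10 mm.
- Node threshold B (Appendix E): at least 20 mm short axis.
- Scans every 12 weeks (calendar notes); 12 patients planned, up to 15 enrolled (13.5).

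**1. One node as the only lesion, 12 mm growing to 17 mm**
- Change: 17 − 12 = 5 mm; 5/12 = 41.7%.
- Under A the node is a target and both parts of the test are met: progression.
- Under B it is non-target. The measured test does not apply, and growth of one lesion is not enough by the non-target standard.

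**2. The reverse: liver lesion 30 to 36 mm, node stable at 18 mm**
- Under A the node enters the sum: 30 + 18 = 48 mm, then 36 + 18 = 54 mm; 6/48 = 12.5%. Not progression.
- Under B the sum is the liver lesion alone: 30 to 36 mm; 6/30 = 20%, and 6 mm. Progression.

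So the direction of disagreement cannot be predicted.

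**3. A node above both thresholds, 22 to 28 mm**
- Change: 6 mm; 6/22 = 27.3%. Progression under A and B. The split is confined to patients whose baseline nodes lie between the two thresholds.

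**4. Appendix E against itself**
- Its opening makes a node pathological above 20 mm. Its description of non-measurable disease uses the same word for nodes of 10 to under 20 mm. Both cannot be the definition.

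**5. Section 13.8 against 13.3**

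| Item | 13.3 | 13.8 |
|---|---|---|
| Soft-tissue criterion | stated | absent |
| Link to bone criterion | *or* | none |
| New bone lesions needed | two or more | two or more |
| Working group cited | 3 | 2 |

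**6. Size of one changed call**
- Scans fall near weeks 12, 24 and 36, and six months is about 26 weeks. A call that moves from week 24 to week 36 crosses six months.
- With no censoring, the six-month proportion changes by 1/12 = 8.3 points, or 1/15 = 6.7 points with 15 patients.

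**7. Primary endpoint**
- The rule of 2 or more PSA50 responses in 12 uses no imaging. Its exact error rate at 3% is 1 − 0.97^12 − 12(0.03)(0.97^11) = 0.0486, and its power at 23% is 1 − 0.77^12 − 12(0.23)(0.77^11) = 0.801. These agree with the stated 5% and 80%, and nothing here changes them.

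**The case against.** The strongest reply is that 13.3 states a necessary condition. A node must exceed 1.0 cm to be target *or* evaluable; that does not make every such node a target. Nodes of 10 to under 20 mm could be evaluable non-targets and larger ones targets, which fits Appendix E. This reading is available, and it rules out saying that every node between 10 and 20 mm changes class. But 13.3 gives no other cut-off for targets, so a site reading it alone has no reason to use 20 mm. The ambiguity stands.

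Other points on that side hold in part:

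- **One new bone lesion versus two.** A reader might infer that Appendix E makes a single new bone lesion progression, against two elsewhere. Sections 7.4.1 and 13.3 use RECIST for soft tissue only, 7.4 lists bone separately, and every bone-specific rule says two or more. What remains is a scoping gap: Appendix E's new-lesion note does not state that limit.
- **A new 15 mm node.** A reader might infer that it counts under 13.3 and not under Appendix E. That does not follow: 13.3 speaks only of baseline nodes, and Appendix E is itself unclear about that size.
- **Working group 2 versus 3.** The documents word the bone rule the same way under both and do not say how they differ. Only a citation mismatch is shown.
- **The missing *or* in 13.8.** This is probably a drafting slip. Section 3.0 sends the reader to 13.2–13.4 for complete endpoint definitions, so 13.3 should prevail over 13.8. No such pointer settles 13.3 against Appendix E.
- **Ending treatment.** The 1.0 cm figure appears only in the statistical section; 7.4 and 7.4.1 both point to Appendix E. The node conflict therefore bears mainly on rPFS scoring.
- **Non-target progression.** Appendix E lets the treating physician's opinion prevail when only non-target lesions progress, so the first example could still be called progression by judgement.

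**Conclusion.** The point holds as an inconsistency in how rPFS is defined. The node thresholds in 13.3 and Appendix E are not reconciled, Appendix E uses *pathological* in two senses, and 13.8 does not reproduce the definition in 13.3. The two worked splits depend on reading 13.3 as a target threshold, which its wording permits but does not require.

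How many patients this would affect cannot be known from the documents, since it depends on how many have baseline nodes between the thresholds that decide progression. The 8.3-point figure (6.7 with 15 patients) is the effect of one changed call that crosses six months, without censoring; it is not an expected bias. A reader might infer that rPFS is biased in a known direction, or that the trial's go-or-no-go decision is affected. Neither follows: the examples run both ways, and the decision rests on PSA50. rPFS is descriptive here, with no test or decision rule. The passages should be corrected because the estimate is meant to be reported and the correction is cheap.

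**What to change.** For the rPFS analysis:

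1. State one node definition, with a short-axis cut-off for target nodes and one for non-target nodes, and use it identically in 13.3 and Appendix E. Use *pathological* in one sense only.
2. Replace the progression wording in 13.8 with the 13.3 definition: soft-tissue progression **or** two or more new bone lesions not consistent with flare.
3. Cite one working-group version in 7.1, 7.4, 7.4.1, 13.3 and 13.8.
4. State that, for rPFS, Appendix E applies to the soft-tissue criterion, as 13.3 already implies.
5. Score all scans for rPFS by that single rule, including those already read.

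Where the same criteria end treatment, the sponsor must reconcile the passages; no stopping rule is proposed here.

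The cost is a wording amendment and a re-score. Stored scans may need re-reading: Appendix E does not require measurement of non-target lesions, so sizes may be missing for nodes that become targets if the lower threshold is adopted. No new imaging is needed.

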# 13.4 Correlative Endpoint Definitions

- Circulating tumor DNA (ctDNA) will be measured in peripheral blood to evaluate changes in mutation patterns, which will be correlated to therapeutic outcomes and compare to any prior noted mutations in germline or somatic sequencing
- γH2AX foci in CTCs and optional FFPE biopsy tissue
- F2-isoprostane levels will be evaluated in urine as a measure of oxidative injury and will be correlated to therapeutic outcomes and toxicities.
- 8-oxo-2'-deoxyguanosine will be evaluated in urine as a measure of oxidative stress and correlated to therapeutic outcomes.

# 13.5 Sample Size/Accrual Rate

Accrual to this study is expected to be one patient per month. For this combination to be considered for further study a  $PSA_{50}$  response of 23% or more would be desirable. Our null hypothesis of 3% is based on the low  $PSA_{50}$  response rate, 3% (1 of 33), reported by Mateo et al. for this patient population. This single-stage design has a 95% chance ( $\alpha$  = 0.05) of rejecting the therapy if the true percentage of patients with some benefit from treatment is less than or equal to 3% and an 80% chance of concluding the therapy is beneficial if the true percentage is 23% or more. Twelve patients, will be assessed for 6 months and if 2 or more achieve a  $PSA_{50}$  response, the therapy will be considered for a larger study. Patients enrolled who never receive any study related therapy will be

replaced. Enrollment would be allowed to continue, up to a maximum of 15 patients, to replace those patients that drop-out early.

# 13.6 Futility and Safety Monitoring Plan

Given the small number of patients and the importance of obtaining correlative data to consider during the final evaluation of the study results, there will be no futility monitoring for efficacy during this pilot study. The trial will however employ a standard safety monitoring plan for adverse events. In addition, if any patient is diagnosed with an adverse event of special interest: myelodysplastic syndrome, acute myeloid leukemia, new primary malignancy (other than MDS/AML) or pneumonitis during the trial, the trial will be paused for a safety review.

Toxicity will be monitored continuously for grade 3-4 adverse events that do not resolve to grade 2 following four-weeks drug discontinuation (per section 8.1). The stopping rule is based on the posterior probability that the combination of treatments is too toxic. If the rate of these toxicities convincingly exceeds 30%, the study PI will hold enrollment if the posterior probability of risk greater than 0.30 is 65% or higher. The prior for this toxicity monitoring rule is beta (2,6). This corresponds to assuming our prior guess for the toxicity rate is 25%, and there is 90% probability that this proportion is between 5% and 52%.

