**Table 9. Monitoring rule for safety.** 

Stop if safety events are seen	2	3	4	5
in N patients	2	3-6	7-9	10-12

The operating characteristics of the stopping rule shows the percent of the time that the monitoring rule would pause the study under different hypothetical risks of toxicity, along with the average sample size (based on 5000 simulations).

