**Table 10. Operating Characteristics for Safety** 

Risk of safety event	0.15	0.25	0.30	0.35	0.40	0.45	0.50
% of Time Study Stops	7.4%	26.5%	39.8%	52.3%	67.8%	78.6%	86.3%
Expected Sample Size	11.5	10.4	9.6	8.7	7.7	6.9	6.1

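### Table 10 treats each patient's safety outcome as known before the next patient enters, so its expected sample sizes are too low for an event that takes onset plus four weeks to classify

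*Combined protocol and SAP*

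**What the plan says.** Section 13.6 states that "Toxicity will be monitored continuously" and that the events counted are "grade 3-4 adverse events that do not resolve to grade 2 following four-weeks drug discontinuation". The prior is Beta(2,6), and "the study PI will hold enrollment if the posterior probability of risk greater than 0.30 is 65% or higher". Table 9 turns this into a boundary: 2 events in 2 patients, 3 in 3-6, 4 in 7-9, 5 in 10-12. The table does not say whether N counts patients enrolled, treated or fully observed.

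Table 10 reports the "percent of the time that the monitoring rule would pause the study under different hypothetical risks of toxicity", with a row headed "Expected Sample Size". It is said to rest on 5000 simulations; no accrual, onset or delay assumption is given. Section 13.5 says "Accrual to this study is expected to be one patient per month". Section 7.6.2 starts ascorbate on day 8 of cycle 1.

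**The concern.** A patient cannot contribute an event until the toxicity has appeared and four weeks off drug have passed. Meanwhile enrolment goes on. If Table 10 ignores this, it describes a faster rule than the one defined in the text above it.

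At stake is how many patients are exposed before a hold. Section 4.2.8 says the two agents have not been combined before to treat this disease, so Table 10 is the plan's only quantitative statement of how quickly this rule would act if the combination were too toxic.

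**Working it through.** **Inputs.** From section 13.6: prior Beta(2,6), threshold P(risk > 0.30) ≥ 0.65, four weeks (28 days) to classify, boundary as in Table 9, maximum 12 patients. From section 13.5: one patient per month (30.4 days). Onset time is not in the documents. It is assumed uniform over 0-4 or 0-12 weeks from first dose.

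**1. Table 9 reproduces.** With x events in n patients the posterior is Beta(2 + x, 6 + n − x). The smallest x giving P(risk > 0.30) ≥ 0.65 matches every printed cell. For example, 2 of 2 gives 0.730 (stop) and 2 of 3 gives 0.6496 (continue).

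**2. Table 10 reproduces with no delay.** Exact sequential binomial recursion: after each patient, update the distribution of x, remove the probability at or above the boundary, and continue to n = 12. Expected N = Σ n·P(cross at n) + 12·P(never cross).

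| True risk | Table 10 | No-delay calculation |
|---|---|---|
| 0.15 | 7.4%, 11.5 | 7.6%, 11.49 |
| 0.25 | 26.5%, 10.4 | 26.9%, 10.35 |
| 0.30 | 39.8%, 9.6 | 40.0%, 9.57 |
| 0.35 | 52.3%, 8.7 | 53.6%, 8.71 |
| 0.40 | 67.8%, 7.7 | 66.5%, 7.81 |
| 0.45 | 78.6%, 6.9 | 77.5%, 6.94 |
| 0.50 | 86.3%, 6.1 | 86.1%, 6.11 |

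All percentages agree within 1.3 points and all expected sample sizes within about 0.1. That Table 10 assumes immediate outcomes is inferred from this match, since the plan does not say so.

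**3. When the no-delay model could hold.** 30.4 − 28 = 2.4 days, so onset would have to fall within about two days of first dose. Ascorbate begun on day 8 is 7 days after entry, and 7 + 28 = 35 days, which is later than 30.4. A toxicity of the combination is therefore classified after the next patient has entered.

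**4. Expected enrolment with delay.** Two readings of N were tested.

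- *Fully followed patients, counted in order (exact).* The status of patient n is known W + 28 days after entry. By then min(12, n + k) patients are enrolled, with k = floor((W + 28)/30.4). For W = 28 days, 56/30.4 = 1.84, so k = 1. For W = 84 days, 112/30.4 = 3.68, so k = 3. Replace n by min(12, n + k) in the step 2 formula.
- *All enrolled (simulation, 20,000 trials per cell).* Each event is counted at entry + onset + 28 days, against everyone enrolled by then.

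| Risk | Stated | In order, 0-4 wk | In order, 0-12 wk | All enrolled, 0-4 wk | All enrolled, 0-12 wk |
|---|---|---|---|---|---|
| 30% | 9.6 | 9.9 | 10.6 | 10.5 | 11.1 |
| 40% | 7.7 | 8.4 | 9.6 | 9.2 | 10.1 |
| 50% | 6.1 | 6.9 | 8.5 | 7.7 | 8.9 |

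A third reading counts events as soon as they are classified, with N the patients classified so far. With onset over 0-1 or 0-3 months, expected enrolment is about 9.9 at 30% risk and 6.8-7.1 at 50%. That is still above the stated values, though by less.

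**5. Percentage stopped at 30% risk (stated 39.8%).**

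- All enrolled: about 31-35%.
- Fully followed, in order: 40.0%, unchanged.
- Events counted on classification: 39.6% (onset 0-1 month), 44.6% (0-3 months), 53.9% (0-6 months).

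**The case against.** **The four weeks alone do nothing.** At evenly spaced monthly entry, onset on day 0 leaves Table 10 intact, so the whole effect rests on an onset time the documents do not give. This stands as to size, which is why a range is shown. It does not rescue the no-delay model, which needs onset within about two days.

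**The day 8 start is not uniform across the documents.** Section 7.6.2 and the calendar footnote put olaparib alone in week 1, but Table 2 lists the first ascorbate dose on day 1 of the cycle, and the Schema has full dose from week 2. These passages must be reconciled. On a day 1 start, classification before the next entry would be possible, but only for onset within about two days.

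**A reader might infer that stopping is also rarer than stated, with pending patients counted as event-free.** The documents do not support this. Table 9 says nothing about who is in N, and the lower percentages follow only if N is all enrolled. Counting fully followed patients in order leaves the crossing probability unchanged, and counting events on classification can raise it.

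**A reader might also infer that the early boundaries lapse before events can be counted.** If N is all enrolled, this is true of 2 of 2 for a combination toxicity: patient 2 is classified no earlier than day 30.4 + 35 = 65.4, after patient 3 enters at day 60.9. It is not true of 3 in 3-6. Patient 7 enters at about day 183. By then patients 1-5 are classified if onset is within 4 weeks (121.8 + 56 = 177.8 days for patient 5), and patients 1-3 if within 12 weeks (60.9 + 112 = 172.9 days for patient 3).

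**Other safeguards exist.** Section 13.6 pauses the trial for any adverse event of special interest, section 9.5.1 requires 24-hour reporting of serious events and unacceptable toxicities, section 12.2 sets regular safety meetings, and section 12.3 adds a Safety Monitoring Committee. These limit the consequence but do not correct the table.

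**Conclusion.** The point holds for expected sample size. The arithmetic in Tables 9 and 10 is sound; the fault is an unstated assumption of immediate outcomes that the plan's own event definition and accrual rate contradict. Under every counting rule tested, more patients are enrolled before a hold than Table 10 states. Across the two readings in the step 4 table, the excess is about 0.3-1.5 patients at 30% risk, 0.7-2.4 at 40% and 0.8-2.8 at 50%.

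These sizes rest on evenly spaced monthly entry, a cap of 12 patients and the assumed onset windows. The direction of any change in the stopping percentage cannot be settled until N is defined.

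**What to change.** - In Table 9, define N as patients whose safety status is known: either an event has been classified, or a fixed observation period has been completed without one. State the length of that period and how patients with a pending status are handled.
- Re-simulate Table 10 at one patient per month, with stated onset assumptions (more than one) and the four-week classification delay.
- Restate both rows, and report the number enrolled at the time of a hold.

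The cost is a short simulation and slightly less favourable figures. The prior and the posterior threshold need not change.
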